11.0 TOXICITIES/SIDE EFFECTS

Toxicities will be assessed via the NCI Common Terminology Criteria for Adverse Events (CTCAE, version 3.0, http://ctep.cancer.gov/forms/CTCAEv3.pdf). All toxicities, grades 1-4, will be recorded in both phases of the protocol until 30 days after the last dose of cetuximab. Any patients consented after the memo sent to participating sites dated December 15, 2010 need to have all grades toxicities collected

The most common side effects expected are alopecia (likely), nausea and vomiting due to RT and/or chemotherapy (likely), myelosuppression (blood product transfusions and need for

hospitalization for fever and neutropenia both possible), infertility (possible), and second malignancies due to RT and/or chemotherapy (unlikely, but very severe should one occur).

Possible risks also include unexpected side effects from the addition of cetuximab to the external beam radiation therapy and chemotherapy.

11.1 RADIATION THERAPY

Acute toxicities: Nausea with or without emesis is an anticipated side effect of radiation therapy and may be treated with antiemetic medications. Fatigue may occur. Patients generally have transient focal alopecia in the radiation field and may have permanent epilation in some regions. Skin erythema is expected but is rarely severe. Temporary xerostomia and dysphagia may occur. Standard supportive care according to institutional guidelines will be delivered in an attempt to ameliorate any of these relevant effects.

Late effects: Common late effects of radiation, depending on the field of radiation, include neurocognitive dysfunction, growth impairment, hearing loss, and endocrine dysfunction (hypothalamic/pituitary, thyroid, and gonadal). Rare but severe late effects may include secondary malignancies (approximately 5%) and necrosis of central nervous system tissue, including brainstem (approximately 1-2%).

[figure not shown]
11.2 CETUXIMAB

Anticipated Adverse Events (all data in this section 11.2 provided by Bristol-Myers Squibb) Please see updated Investigators brochure dated 10/21/2010

Squamous Cell Cancer of the Head and Neck

Except where indicated, the data described below reflect exposure to cetuximab in 208 patients with locally or regionally advanced SCCHN who received cetuximab in combination with radiation and as monotherapy in 103 patients with recurrent or metastatic SCCHN. Of the 103 patients receiving cetuximab monotherapy, 53 continued to a second phase with the combination of cetuximab plus chemotherapy. Patients receiving cetuximab plus radiation therapy received a median of 8 doses (range 1-11 infusions). The population had a median age of 56; 81% were male and 84% Caucasian. Patients receiving cetuximab monotherapy, received a median of 11 doses (range 1-45 infusions). The population had a median age of 57; 82% were male and 100% Caucasian. The most serious adverse reactions associated with cetuximab in combination with radiation therapy in patients with head and neck cancer were:

- Infusion reaction (3%)
- Cardiopulmonary arrest (2%)
- Dermatologic toxicity (2.5%)
- Mucositis (6%)
- Radiation dermatitis (3%)
- Confusion (2%)
- Diarrhea (2%)

Fourteen (7%) patients receiving cetuximab plus radiation therapy and 5 (5%) patients receiving cetuximab monotherapy, discontinued treatment primarily because of adverse events.

The most common adverse events seen in 208 patients receiving cetuximab in combination with radiation therapy were acneform rash (87%), mucositis (86%), radiation dermatitis (86%), weight loss (84%), xerostomia (72%), dysphagia (65%), asthenia (56%), nausea (49%), constipation (35%), and vomiting (29%).

The most common adverse events seen in 103 patients receiving cetuximab monotherapy were acneform rash (76%), asthenia (45%), pain (28%), fever (27%), and weight loss (27%).

The data in the table below are based on the experience of 208 patients with locoregionally advanced SCCHN treated with cetuximab plus radiation therapy compared to 212 patients treated with radiation therapy alone [Cetuximab package insert. ImClone Systems Incorporated and Bristol-Myers Squibb Company 2006. ER-B0001-03-06].

Incidence of selected adverse events ($\geq 10\%$) in patients with loco-regionally advanced SCCHN

	Cetuximab plus Radiation (n=208)		Radiation Therapy Alone (n=212)	
Body System	Grades 1 – 4	Grades 3 and 4	Grades 1–4	Grades 3 and 4
Preferred Term		% of P	atients	
Body as a Whole				
Asthenia/Malaise	56	4	48	5
Fever ¹	29	1	13	<1
Headache	19	<1	8	<1
Infusion Reaction ²	15	3	2	0
Infection	13	1	9	1
Chills ¹	16	0	5	0
Digestive				
Mucositis/Stomatitis	93	56	94	52
Xerostomia	72	5	71	3
Dysphagia	65	26	63	30
Nausea	49	2	37	2

Constipation	35	5	30	5
Vomiting	29	2	23	4
Anorexia	27	2	23	2
Diarrhea	19	2	13	1
Dyspepsia	14	0	9	1
Metabolic/Nutritional				
Weight Loss	84	11	72	7
Dehydration	25	6	19	8
Respiratory				
Pharyngitis	26	3	19	4
Cough Increased	20	<1	19	0
Skin/Appendages				
Acneform Rash ³	87	17	10	1
Radiation Dermatitis	86	23	90	18
Application Site Reaction	18	0	12	1
Pruritus	16	0	4	0

¹ Includes cases also reported as infusion reactions

² Infusion reaction is defined as any event described at any time during the clinical study as "allergic reaction" or "anaphylactoid reaction" or any event on the first day of dosing described as "allergic reaction",

"anaphylactoid reaction", "fever", "chills", "chills and fever" or "dyspnia".

³ Acneform rash as defined as any event described as "acne", "rash", "maculopapular rash", "pustular rash", "dry skin" or "exfoliative dermatitis".

Late Radiation Toxicity

The overall incidence of late radiation toxicities (any grade) was higher in cetuximab in combination with radiation therapy compared with radiation therapy alone. The following sites were affected: salivary glands (65% versus 56%), larynx (52% versus 36%), subcutaneous tissue (49% versus 45%), mucous membrane (48% versus 39%), esophagus (44% versus 35%), skin (42% versus 33%), brain (11% versus 9%), lung (11% versus 8%), spinal cord (4% versus 3%), and bone (4% versus 5%). The incidence of Grade 3 or 4 late radiation toxicities were generally similar between the radiation therapy alone and the cetuximab plus radiation treatment groups.

Colorectal Cancer

Except where indicated, the data described below reflect exposure to cetuximab in 774 patients with advanced metastatic colorectal cancer. Cetuximab was studied in combination with irinotecan (n=354) or as monotherapy (n=420). Patients receiving cetuximab plus irinotecan received a median of 12 doses [with 88/354 (25%) treated for over 6 months], and patients receiving cetuximab monotherapy received a median of 7 doses [with 36/420 (9%) treated for over 6 months]. The population had a median age of 59 and was 59% male and 91% Caucasian. The range of dosing for patients receiving cetuximab plus irinotecan was 1-84 infusions, and the range of dosing for patients receiving cetuximab monotherapy was 1-63 infusions.

The most **serious adverse reactions** associated with cetuximab were:

- Infusion reaction (3%)
- Dermatologic toxicity (1%)
- Interstitial lung disease (0.4%)
- Fever (5%)
- Sepsis (3%)
- Kidney failure (2%)
- Pulmonary embolus (1%)
- Dehydration (5%) in patients receiving cetuximab plus irinotecan, 2% in patients receiving cetuximab monotherapy
- Diarrhea (6%) in patients receiving cetuximab plus irinotecan, 0.2% in patients receiving cetuximab monotherapy

Thirty-seven (10%) patients receiving cetuximab plus irinotecan and 17 (4%) patients receiving cetuximab monotherapy discontinued treatment primarily because of adverse events.

The most common adverse events seen in 354 patients receiving cetuximab plus irinotecan were acneform rash (88%), asthenia/malaise (73%), diarrhea (72%), nausea (55%), abdominal pain (45%), and vomiting (41%).

The most common adverse events seen in 420 patients receiving cetuximab monotherapy were acneform rash (90%), asthenia/malaise (48%), nausea (29%), fever (27%), constipation (26%), abdominal pain (26%), headache (26%), and diarrhea (25%).

Because clinical trials are conducted under widely varying conditions, adverse reaction rates observed in the clinical trials of a drug cannot be directly compared to rates in the clinical trials of another drug and may not reflect the rates observed in practice. The adverse reaction information from clinical trials does, however, provide a basis for identifying the adverse events that appear to be related to drug use and for approximating rates.

Data in patients with advanced colorectal carcinoma in the table below are based on the experience of 354 patients treated with cetuximab plus irinotecan and 420 patients treated with cetuximab monotherapy.

Infusion Reactions

Severe infusion reactions occurred with the administration of cetuximab in approximately 3%

		olus Irinotecan (354)	Cetuximab Monotherapy (n=420)					
Body System	Grades 1 - 4	Grades 3 and 4	Grades 1 – 4	Grades 3 and 4				
Preferred Term ¹	Grades 1 - 4	% of Patients						
Body as a Whole								
Asthenia/Malaise ²	73	16	48	10				
Abdominal Pain	45	8	26	9				
	34	4	20	<1				
Fever ³								
Pain	23	6	17	5				
Infusion Reaction ⁴	19	3	21	2				
Infection	16	1	14	1				
Back Pain	16	3	10	2				
Headache	14	2	26	2				
Digestive								
Diarrhea	72	22	25	2				
Nausea	55	6	29	2				
Vomiting	41	7	25	3				
Anorexia	36	4	23	2				
Constipation	30	2	26	2				
Stomatitis	26	2	10	<1				
Dyspepsia	14	0	6	0				
Hematic/Lymphatic								
Leukopenia	25	17	<1	0				
Anemia	16	5	9	3				
Metabolic/Nutritional								
Weight Loss	21	0	7	1				
Peripheral Edema	16	1	10	1				
Dehydration	15	6	10	3				
Nervous								
Insomnia	12	0	10	<1				
Depression	10	0	7	0				
Respiratory								
Dyspnea ³	23	2	17	7				
Cough Increased	20	0	11	1				
Skin/Appendages								
Acneform Rash	88	14	90	8				
Alopecia	21	0	4	0				
Skin Disorder	15	1	4					
Nail Disorder	13	<1	4 16					
Pruritus	12	1	10	<1				
Conjunctivitis	10		7	<1				
¹ Adverse events that occurred			/	-				

Incidence of Adverse Events (≥10%) in Patients with Advanced Colorectal Carcinoma

Adverse events that occurred (toxicity Grades 1 through 4) in $\geq 10\%$ of patients with refractory colorectal carcinoma treated with cetuximab plus irinotecan or in $\geq 10\%$ of patients with refractory colorectal carcinoma treated with cetuximab monotherapy.

 2 Asthenia/malaise is defined as any event described as "asthenia", "malaise", or "somnolence".

³ Includes cases reported as infusion reaction.

⁴ Infusion reaction is defined as any event described at any time during the clinical study as "allergic reaction" or "anaphylactoid reaction", or any event occurring on the first day of dosing described as "allergic reaction", "anaphylactoid reaction", "fever", "chills", "chills and fever" or "dyspnea".

⁵ Acneform rash is defined as any event described as "acne", "rash", "maculopapular rash", "pustular rash", "dry skin", or "exfoliative dermatitis".

Amended: 04/10/12

(46/1485) of patients, rarely with fatal outcome (<1 in 1000). Approximately 90% of severe infusion reactions were associated with the first infusion of cetuximab despite the use of prophylactic antihistamines. These reactions were characterized by the rapid onset of airway obstruction (bronchospasm, stridor, hoarseness), urticaria, hypotension, and/or cardiac arrest. Caution must be exercised with every cetuximab infusion, as there were patients who experienced their first severe infusion reaction during later infusions. A 1-hour observation period is recommended following the cetuximab infusion. Longer observation periods may be required in patients who experience infusion reactions.

A 20-mg test dose was administered intravenously over 10 minutes prior to the initial dose to all patients in earlier studies. The test dose did not reliably identify patients at risk for severe allergic reactions.

In the Southeastern region of the United States a higher number of infusion-related anaphylactic reactions to cetuximab have been reported in adult studies than in other areas of the United States [J Clin Oncol 2007, 25:3644-3648 and N Engl J Med 2008, 358:1109-1117].

Pulmonary Toxicity

Interstitial lung disease (ILD) was reported in 3 of 774 (<0.5%) patients with advanced colorectal cancer and in 1 of 796 patients with head and neck cancer receiving cetuximab. Among these four cases, interstitial pneumonitis with non-cardiogenic pulmonary edema resulting in death was reported in one patient with colon cancer. In two of the remaining cases, the patients had pre-existing fibrotic lung disease and experienced an acute exacerbation of their disease while receiving cetuximab in combination with irinotecan. The onset of symptoms occurred between the fourth and eleventh doses of treatment in all reported cases. In the event of acute onset or worsening pulmonary symptoms, cetuximab therapy should be interrupted and a prompt investigation of these symptoms should occur. If ILD is confirmed, cetuximab should be discontinued and the patient should be treated appropriately [Cetuximab package insert. ImClone Systems Incorporated and Bristol-Myers Squibb Company 2006. ER-B0001-03-06].

Dermatologic Toxicity

In cynomolgus monkeys, cetuximab, when administered at doses of approximately 0.4 to 4 times the weekly human exposure (based on total body surface area), resulted in dermatologic findings, including inflammation at the injection site and desquamation of the external integument.¹ At the highest dose level, the epithelial mucosa of the nasal passage, esophagus, and tongue were similarly affected, and degenerative changes in the renal tubular epithelium occurred. Deaths due to sepsis were observed in 50% (5/10) of the animals at the highest dose level beginning after approximately 13 weeks of treatment.

In clinical studies of cetuximab, dermatologic toxicities, including acneform rash, skin drying and fissuring, and inflammatory and infectious sequelae (eg, blepharitis, cheilitis, cellulitis, cyst) were reported. In patients with advanced colorectal cancer, acneform rash was reported in 89% (686/774) of all treated patients, and was severe (Grade 3 or 4) in 11% (84/774) of these patients. Subsequent to the development of severe dermatologic toxicities, complications including *S. aureus* sepsis and abscesses requiring incision and drainage were reported.

IRB#: 09-014 A(7)

Non-suppurative acneform rash described as "acne", "rash", "maculopapular rash", "pustular rash", "dry skin", or "exfoliative dermatitis" was observed in patients receiving cetuximab plus irinotecan or cetuximab monotherapy. One or more of the dermatological adverse events were reported in 88% (14% Grade 3) of patients receiving cetuximab plus irinotecan and in 90% (8% Grade 3) of patients receiving cetuximab monotherapy. Acneform rash most commonly occurred on the face, upper chest, and back, but could extend to the extremities and was characterized by multiple follicular- or pustular-appearing lesions. Skin drying and fissuring were common in some instances, and were associated with inflammatory and infectious sequelae (eg, blepharitis, cellulitis, cyst). Two cases of *S. aureus* sepsis were reported. The onset of acneform rash was generally within the first two weeks of therapy. Although in a majority of the patients the event resolved following cessation of treatment, in nearly half of the cases, the event continued beyond 28 days.

A related nail disorder, occurring in 14% of patients (0.4% Grade 3), was characterized as a paronychial inflammation with associated swelling of the lateral nail folds of the toes and fingers, with the great toes and thumbs as the most commonly affected digits.

Cetuximab Use With Radiation Therapy

The safety of cetuximab in combination with radiation therapy and Cisplatin has not been established. Death and serious cardiotoxicity were observed in a 21 patient single-arm study of patients with locally advanced squamous cell cancer of the head and neck. Patients received cetuximab, delayed, accelerated (concomitant boost) fractionation radiation therapy and Cisplatin (100 mg/m²) [Cetuximab package insert. ImClone Systems Incorporated and Bristol-Myers Squibb Company 2006. ER-B0001-03-06].

In a randomized, controlled trial in patients with squamous cell carcinoma of the head and neck (SCCHN), cardiopulmonary arrest and/or sudden death occurred in 4/208 patients (2%) treated with radiation therapy and cetuximab as compared to none of 212 patients treated with radiation therapy alone. Three patients with prior history of coronary artery disease died at home, with myocardial infarction as the presumed cause of death. One of these patients had arrhythmia and one had congestive heart failure. Death occurred 27, 32, and 43 days after the last dose of cetuximab. One patient with no prior history of coronary artery disease died one day after the last dose of cetuximab.

Electrolyte Depletion

In 244 patients evaluated in ongoing, controlled clinical trials, the incidence of hypomagnesemia, both overall and severe, was increased in patients receiving cetuximab alone or in combination with chemotherapy as opposed to those receiving best supportive care or chemotherapy alone. Approximately one-half of these patients receiving cetuximab experienced hypomagnesemia and 10-15% experienced severe hypomagnesemia¹.

Cardiac Toxicity

Cardiac arrest and / or sudden death occurred in 2% (4/208) of patients with squamous cell carcinoma of the head and neck treated with radiation therapy and cetuximab as compared to none of 212 patients treated with radiation therapy alone. Fatal events occurred within 1 to 43 days after the last Cetuximab treatment. Cetuximab in combination with radiation therapy should be used with caution in head and neck cancer patients with known coronary artery disease,

congestive heart failure, and arrhythmias. Although the etiology of these events is unknown, close monitoring of serum electrolyte, including serum magnesium, potassium and calcium, during and after Cetuximab therapy is recommended.

11.3 IRINOTECAN

Common Dermatologic: Alopecia Hematologic: Drug-induced eosinophilia

Serious

Gastrointestinal: Diarrhea, Nausea and Vomiting Hematologic: Leukopenia, Neutropenia, Thrombocytopenia, Lymphopenia Hepatic: Decreased liver function Respiratory: Interstitial lung disease

12.0 CRITERIA FOR THERAPEUTIC RESPONSE/OUTCOME ASSESSMENT

The study's primary aim is to increase the proportion of patients achieving 1-year progression-free survival. Progression-free is defined as lack of unequivocal tumor progression or treatmentassociated death. Unequivocal tumor progression will be determined (usually via brain MRI) by a POETIC institutional radiologist. If radiological studies suggest possible, but not unequivocal progression, the patient may remain on study until unequivocal progression has been determined. In select cases biopsy may be necessary to distinguish tumor recurrence from radiation effect.

In this study, we will compare the product of 2-dimensional measures of the tumor on the baseline and follow-up MRI scans. Modified Macdonald criteria will be used [J Clin Oncol 1990; 8:1277-1280]. Responses will be defined as:

Complete response: Complete resolution of all tumor.

Partial response: \geq 50% decrease in the 2-dimensional size of the tumor.

Stable disease: < 50% decrease to < 25% increase in the 2-dimensional size of the tumor.

Progressive disease: $(1) \ge 25\%$ increase in the 2-dimensional size of the tumor, or (2) any new tumor focus, or (3) worsening neurological status that cannot be explained by any other cause associated with increase in tumor size (but < 25%).

Determination of favorable responses will be made via comparison to the baseline MRI, while determination of progressive disease will be via comparison to the nadir

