2.0 OBJECTIVES AND SCIENTIFIC AIMS

Primary objectives:

- 1. To determine the proportion of patients with high-grade astrocytoma and diffuse pontine tumors achieving one year progression free survival.
- 2. To determine the safety of cetuximab administered weekly in conjunction with involved field external beam radiation therapy for diffuse pontine tumors and high-grade astrocytomas.

Secondary objectives:

- 1. To estimate the response rate, time to progression, and overall survival in 2 cohorts of patients (diffuse intrinsic pontine tumors, high-grade astrocytomas) treated on this protocol.
- 2. To explore whether there are any potential associations between primary tumor tissue molecular markers and tumor response.
- 3. To identify CSF protein markers that might indicate the presence of a brain tumor, to validate proteomic methodology by correlating protein and ELISA measurements of known proteins implicated in angiogenesis and tumor progression (VEGF, bFGF, SPARC, attractin), and to explore whether there are any potential associations between histology (grade) with protein and ELISA measurements of those proteins.
- 4. To investigate whether the rash associated with cetuximab is secondary to an inflammatory pathway initiated and mediated by the action of cetuximab on host cells.

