14.0 BIOSTATISTICS

14.1 DEFINITION OF ENDPOINTS

The primary endpoint of this study is progression free survival at one year. Progression will be measured from initiation of therapy until first documented progression of disease. Death or the unlikely event of loss to follow-up, within one year will also be counted as progression. Those who are alive and progression free one year after initiation of therapy will be considered treatment successes for the evaluation of the primary endpoint.

Response is considered as a secondary endpoint. All patients who have initiated therapy will be evaluated for response. Only patients who were declared ineligible and removed prior to receiving any treatment will be excluded.

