14.1.1 DIFFUSE PONTINE TUMORS

For this group of patients the goal is to effectively discriminate between progression free survival rates at one year of $\leq 10\%$ and $\geq 30\%$ using a single stage design.

The progression free proportion is deemed unacceptable if it is lower than 10% and is promising if greater than 30%. The null hypothesis that the proportion progression free at one year (p) is less than or equal to 0.10 (H0: $p \le 0.10$) will be tested against the alternative hypothesis that p is greater than or equal to 0.30 (H1: $p \ge 0.30$). For this group of tumors, we will accrue 25 patients. If 6 or more are alive and progression free at one year, the treatment will be declared effective and worthy of further testing. If 5 or fewer are alive and progression free at one year, then this group of the trial will be declared to have a negative result. This design yields $\ge 80\%$ probability of a positive result if the true percentage of patients alive and progression free at one year is $\ge 30\%$ (80% power). It yields $\ge 95\%$ probability of a negative result if the true percentage is $\le 10\%$ (5% type I error).

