14.3 SECONDARY BIOLOGICAL AIMS

14.3.1 Progression free and overall survival will be calculated using the methods of Kaplan and Meier, separately for the diffuse pontine and high-grade groups. The response rates will be provided along with their 95% confidence intervals for all patients receiving any study medication or radiation.

14.3.2 It is not known how many patients will agree to participate in the components of the study involving (1) correlation of molecular markers and tumor response to therapy, (2) CSF proteomics, and (3) serum inflammatory cytokine levels. These endpoints are exploratory in nature and any analyses will be purely descriptive. Continuous endpoints will be summarized using medians and ranges, categorical data will be tabulated. Changes in measurements will be given in terms of percent change from baseline and change in absolute value.

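### Section 12.0 leaves non-treatment deaths out of the progression-free definition, contradicting 14.1; the one-year test is safe, but the Kaplan-Meier PFS in 14.3.1 is exposed

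*Combined protocol and SAP*

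**What the plan says.** Section 12.0 names one-year progression-free survival as the study's primary aim and then defines the state: "Progression-free is defined as lack of unequivocal tumor progression or treatmentassociated death". It adds how progression is called: "Unequivocal tumor progression will be determined (usually via brain MRI) by a POETIC institutional radiologist". It does not mention deaths from tumor, deaths from unrelated causes, or loss to follow-up.

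Section 14.1 defines the statistical endpoint. The clock is set by "Progression will be measured from initiation of therapy until first documented progression of disease". It continues: "Death or the unlikely event of loss to follow-up, within one year will also be counted as progression". No cause of death is excluded. Success is then defined: "Those who are alive and progression free one year after initiation of therapy will be considered treatment successes". The decision rules in 14.1.1 and 14.1.2 repeat the requirement to be both alive and free of progression.

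Section 14.3.1 plans the time-to-event analysis: "Progression free and overall survival will be calculated using the methods of Kaplan and Meier", separately for the two groups. It gives no event rule and no censoring rule. Secondary objective 1 in section 2.0 reads "To estimate the response rate, time to progression, and overall survival in 2 cohorts of patients", so it uses a third term, time to progression, which 14.3.1 does not pick up.

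**The concern.** The same phrase has two meanings in one document. Consider a pontine patient who declines and dies between scans, with no reading of unequivocal progression, and whose death is attributed to tumor. Under 12.0 this patient never had an event. Under 14.1 the patient failed.

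Such a patient is plausible under this protocol:

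- Section 10.0 places on-treatment MRI in cycles 3, 6 and 9 of roughly 21-day cycles, so about 3 x 21 = 63 days apart.
- Section 12.0 lets a patient with possible but not unequivocal progression stay on study until the matter is settled.
- Section 12.0 accepts neurological worsening as progression only together with some increase in tumor size.
- The post-treatment scan schedule in section 10.0 is written for patients who complete protocol therapy.

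At stake is the reported PFS curve. A death from the disease itself is not an independent reason to stop observing a patient. Treating it as censoring assumes that the patient had the same outlook as those still at risk, which is plainly untrue. The 12.0 wording also asks someone to judge whether each death was treatment-associated. In a single-arm study that adds a subjective step, which an any-death rule avoids.

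**Working it through.** **Step 1: the plan's own design figures.** The inputs are in 14.1.1 (25 patients, success at 6 or more, 10% against 30%) and 14.1.2 (26 patients, success at 14 or more, 35% against 60%). The formula is the exact binomial upper tail, P(X >= r | n, p).

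| Group | Rule | Type I error at the null | Power at the alternative |
|---|---|---|---|
| Pontine | 6 of 25 | P(X >= 6 \| 25, 0.10) = 0.0334 | P(X >= 6 \| 25, 0.30) = 0.8065 |
| High-grade astrocytoma | 14 of 26 | P(X >= 14 \| 26, 0.35) = 0.0377 | P(X >= 14 \| 26, 0.60) = 0.8007 |

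Both meet the stated limits of 5% and 80%.

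**Step 2: each outcome within one year under each rule.**

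| Outcome within one year | Event under 12.0 | Event under 14.1 | Success in the decision rule |
|---|---|---|---|
| Documented unequivocal progression | yes | yes | no |
| Treatment-associated death, no progression | yes | yes | no |
| Tumor death, progression not documented | no | yes | no, not alive |
| Unrelated death, no progression | no | yes | no, not alive |
| Lost to follow-up, no progression seen | not addressed | yes | no, counted as progression by 14.1 |
| Alive, no progression | no | no | yes |

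The two definitions part company in rows 3 to 5. The last column does not change with the definition for rows 3 and 4, because the decision rule asks separately whether the patient is alive. Row 5 is settled by 14.1 alone. The figures in step 1 therefore stand whether or not 12.0 is corrected.

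**Step 3: the Kaplan-Meier curve.** The estimate is S(t) = product over event times up to t of (1 - d/n), with d events among n at risk. Take one death of the kind in row 3 or 4, with n at risk just before it, no tied event, and the date of death as the censoring date under 12.0.

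- Any death is an event: the curve is multiplied by (n - 1)/n.
- Section 12.0 rule: the curve is multiplied by 1, and the patient leaves the risk set.

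The risk set afterwards is the same. From that time on, the 12.0 curve is higher by the factor n/(n - 1). The smallest possible factor is at full accrual: 25/24 = 1.042 (pontine) and 26/25 = 1.040 (astrocytoma). It grows as the risk set shrinks. For several such deaths the factors multiply. The documents give neither the number of such deaths nor the risk sets at which they would fall, so the total cannot be computed. Only its direction is certain: upward, or zero if no such death occurs.

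**Step 4: does 14.1 already settle 14.3.1?** Only in part. The sentence on death in 14.1 is limited to the first year and serves the one-year endpoint. A Kaplan-Meier curve runs on past one year, and for later deaths no rule is given except the one in 12.0.

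**The case against.** The strongest defence is that the sections can be read together. Section 12.0 tells investigators how to call progression. Section 14.1 carries the endpoint definition, and its wording on death is additive. Death is captured in any case, since it is an off-study criterion in 13.2 and overall survival is analysed. An analyst working from section 14 would naturally treat death as an event in the PFS curve as well.

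For the primary endpoint this defence succeeds. A reader might infer from the conflict that type I error is inflated, since each cohort's decision turns on one patient (6 against 5 of 25; 14 against 13 of 26). The documents do not support that. To gain a success from row 3 or 4, someone would have to count a dead patient as alive, against the plain terms of 14.1, 14.1.1 and 14.1.2.

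A reader might also infer that the 12.0 event fails to match the historical event-free survival rates in sections 3.2 and 3.4. The documents do not define the events behind those rates, and the test uses 14.1, so nothing follows.

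The defence does not rescue the sentence in 12.0. That sentence does more than describe how progression is called: it names which deaths count, and it leaves most causes out. Nor does the defence fully settle 14.3.1, for the reason in step 4.

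**Conclusion.** The definition in 12.0 is wrong as written and contradicts 14.1. The primary go/no-go test, its sample sizes and its cut-offs are unaffected. The finding is confined to the Kaplan-Meier PFS in 14.3.1 and to how sites classify outcome if they work from 12.0.

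If 12.0 were used for the curve, each tumor or other non-treatment death without documented progression would raise the later part of the curve by at least about 4% in relative terms. This rests on the death date being the censoring date. The total effect is unknown because the number of such deaths is unknown. If the analyst applies an any-death rule throughout, there is no bias at all. The point is a moderate consistency correction.

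**What to change.** - **Section 12.0.** Replace the definition with the 14.1 rule: a PFS event is the first of documented progression or death from any cause; for the one-year binary endpoint, loss to follow-up within one year is also a failure. The second clause is needed, because without it 12.0 and 14.1 would still disagree.
- **Section 14.3.1.** State that Kaplan-Meier PFS counts progression or death from any cause as the event, at any time and not only in the first year. State how patients without an event are censored, including those lost to follow-up. If they are censored in the curve but failed in the binary endpoint, say so, because the two one-year figures can then differ.
- **Secondary objective 1 (optional).** Either replace time to progression with PFS, or keep it and define it in 14.3.1 as a separate quantity.

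The cost is a wording amendment. It needs no new data and no change to sample size, cut-offs, type I error or power. The one downside is that reported PFS may look slightly less favorable than it would under 12.0.
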